### 7.1. Primary Efficacy Analyses

#### 7.1.1. Endpoint / Variables

The primary efficacy analyses endpoint is the time to first clinically significant exacerbation within Part C relative to the date of first dose of double-blind treatment [see Section 11.6.1, Part C study day].

Clinically significant exacerbations will be defined as worsening of asthma which requires use of systemic corticosteroids and/or hospitalisation and/or Emergency Department (ED) visits.

For all subjects, i.v. or oral corticosteroid (e.g., prednisone) for at least 3 days or a single intramuscular (IM) corticosteroid dose is required. For subjects on maintenance systemic corticosteroids, at least double the existing maintenance dose for at least 3 days is required.

Exacerbations will only be included within the primary efficacy analyses if supported by objective assessments of asthma deterioration, as reviewed by the Exacerbation Verification Process (see Section 7.1.5.2).

For consistency, exacerbations separated by less than 7 days will be treated as a continuation of the same exacerbation (see Section 11.6.3). Handling of missing or partial dates in reported exacerbations is detailed within Section 11.7.2.1.

#### 7.1.2. Summary Measure

The hazard ratio (Mepolizumab 100mg SC / Placebo) will be the summary measure used for the treatment comparison.

#### 7.1.3. Population of Interest

The population of interest is represented by the randomization inclusion/exclusion criteria of the study and therefore the primary efficacy analyses will be based on the Intent-to-Treat (ITT) [Part C] population, unless otherwise specified.

#### 7.1.4. Strategy for Intercurrent (Post-Randomization) Events

A hypothetical estimand strategy will be applied in the handling of the intercurrent event of discontinuation of double-blind treatment. The treatment effect therefore refers to the outcome if all patients had continued to take double-blind treatment.

Only the On-treatment (Part C) period will be used in the analysis and subjects will be analysed according to the treatment each subject received for more than 50% of injections within Part C (see Section 5.1).

All subjects will be considered to be at risk from their first dose of double-blind treatment at visit C1. Subjects who complete Part C will be considered to be at risk up to their Week 52 (Exit Visit/C14) visit date. Subjects who discontinued double-blind treatment prior to experiencing an exacerbation (event) will be censored at the time of treatment discontinuation [see On-treatment (Part C) definition within Section 11.4.2].

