10.3. Data Analysis Considerations

10.3.1. Analysis Populations

All Subjects Enrolled (ASE) Population

The ASE population will comprise all subjects enrolled and for whom a record exists on the study database. This population will be used for summarising reasons for screen and run-in failures and to report data collected within the variable open-label run-in (Part A) and fixed run-in (Part B).

Intent-to-Treat (ITT) Population

This population will consist of all randomized subjects who receive at least one dose of double-blind study medication, and will be the primary population for all analyses of efficacy and safety data. In cases where there is a discrepancy between the treatment to which a subject was randomized and the treatment they actually received a profile of the subjects' data will be produced.

Per Protocol (PP) Population

The PP population will consist of all subjects in the ITT population who have not been identified as full protocol deviators with respect to criteria that are considered to impact the primary efficacy analysis. The decision to exclude a subject from the PP Population or exclude part of their data from the PP Population analyses will be made prior to breaking the blind. The PP population will be used for a supplementary analysis of the primary endpoint.

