1 - All analyses of Part C and Part D data will be analysed according to the treatment each subject received for more than 50% of injections within Part C (see Section 5.1).

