**NOTES:**

1. Parts A/B and Part D are open-label treatment periods where all subjects received mepolizumab 100mg SC and therefore treatment group descriptions/assignments are not required for RandAll NG

Within displays summarising Part C and Part D, data will be presented according to the treatment each subject received for more than 50% of injections within Part C.

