##### 7.1.5.1. Statistical Methodology Specification

Endpoint / Variables

 
Time to first clinically significant exacerbation (ADaM Dataset: ADTTE)
 

Model Specification

 
The endpoint will be compared between treatment groups using a Cox proportional hazards model. 
 
Fixed Categorical Covariates: Treatment, Region, Baseline maintenance OCS use [Visit C1]
 
Fixed Continuous Covariates: Exacerbations in the year prior to randomization [Visit C1] (as an ordinal variable)
 
 
 
See Section 5.4.1 for further details around model covariates.
 

Model Checking & Diagnostics

 
The TIES=EXACT option will be applied for the handling of ties in failure times.
 
In the event that this model fails to converge, the list of covariates may be adjusted and/or reduced.
 
Distributional assumptions underlying the model used for analysis will be examined by: 
 
assessing if a sufficient number of events occurred within covariate categories.
 
 
 
The proportional hazards assumptions will be examined by: 
 
obtaining plots of the Kaplan-Meier curves and of the log of the cumulative hazard function (log of the negative log of the estimated survivor function) against the log of the survival time
 
 
 
If there are any major important departures from the distributional or proportional hazard assumptions transformations of covariates may be considered or alternative models may be explored as supportive analysis.
 

Model Results Presentation

 
Summaries and graphs will be produced presenting the probability of an event over time by treatment group using Kaplan-Meier estimates and the corresponding 95% confidence intervals.
 

• The hazard ratio (Mepolizumab/Placebo) from the Cox proportional hazards model will be reported with the corresponding 95% CI and p-value.

Sensitivity and Supportive Analyses

• A supportive analysis of the Per Protocol (PP) population will also be performed.

Subgroup Analyses

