#### 7.2.2.1. Statistical Methodology Specification

Endpoint / Variables

 
Ratio to baseline in blood eosinophil count at weeks 12, 24, 36 and 52 (ADaM Dataset: ADLB)
 
See Section 5.2 for further details regarding baseline and change from baseline derivations.
 
See Section 11.6.3 for additional details regarding handling blood eosinophil data.
 

Summary Measure

 
Mean treatment difference at weeks 12, 24, 36 and 52 (Exit Visit/C14)
 

Strategy for Intercurrent (Post-Randomization) Events

 
A hypothetical estimand strategy will be applied in the handling of the intercurrent event of discontinuation of double-blind treatment. The treatment effect therefore refers to the outcome if all patients had continued to take double-blind treatment.
 
Only the On-treatment (Part C) period will be used in the analysis and subjects will be analysed according to the treatment received for more than 50% of injections within Part C (see Section 5.1).
 
All subjects will be considered on-treatment from their first dose of double-blind treatment at visit C1. Subjects who complete Part C will be considered on-treatment up to their Week 52 (Exit Visit/C14) visit date. Subjects who discontinued double-blind treatment will be considered on-treatment until the time of treatment discontinuation. 
 
Blood Eosinophils: see On-treatment (Part C) definition within Section 11.4.3
 
 
 

Model Specification

 
Endpoint will be analysed using a mixed model repeated measures (MMRM) model
 
A log transformation will be applied to blood eosinophil count data prior to analysis.
 
Terms fitted in the MMRM model will include: 
 
Fixed Categorical Covariates: Treatment, Region, Baseline maintenance OCS use [Visit C1], Visit, Visit * Treatment Interaction
 
Fixed Continuous Covariates: Baseline, Exacerbations in the year prior to randomization [Visit C1] (as an ordinal variable), Visit * Baseline
 
Repeated: Visit
 
 
 
See Section 5.4.1 for further details around model covariates.
 

Model Checking & Diagnostics

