## 11. APPENDICES

### 11.1. Appendix 1: Protocol Deviation Management and Definitions for Per Protocol Population

#### 11.1.1. Exclusions from Per Protocol Population

As detailed in Section 4.1 protocol deviations will be tracked by the study team throughout the conduct of the study in accordance with the Protocol Deviation Management Plan (PDMP) and important protocol deviations (including deviations related to study inclusion/exclusion/randomization criteria, conduct of the trial, patient management or patient assessment) will be listed and summarised.

Subjects with protocol deviations considered to potentially have an effect on efficacy will be removed from the Per Protocol (PP) population. Determination of the Per Protocol population will be performed whilst blinded to treatment, before the database is frozen. The reason for the exclusion of any subject will be documented.

A further review of the Per Protocol population will be performed following unblinding regarding protocol deviation criteria impacted by blinded study treatment (e.g. exclusion criteria number 5 below). Similarly the reason for the exclusion of any subject will be documented.

A subject meeting any of the following criteria will be excluded from the Per Protocol population:

Number	Exclusion Description
01	Randomization Inclusion Criterion #1 – Any subject without documented evidence of at least 3 years (156 weeks) of treatment with mepolizumab, with no treatment gaps of greater than 12 weeks (84 days) between any two doses at the time of randomization. See Section 11.6.2 for further details regarding the definition of continuous mepolizumab treatment.
02	Randomization Inclusion Criterion #3 – Any subject with changes in the dose or regimen of ICS, and/or additional controller medication during the fixed run-in period (Part B). N.B. This excludes the use of OCS for the treatment of an asthma exacerbation.
03	Any subject with changes in the dose or regimen of ICS, and/or additional controller medication during double-blind treatment (Part C). N.B. This excludes the use of OCS for the treatment of an asthma exacerbation.
04	Breaking of the treatment blind at any point during Part C of the study.
05	Receiving the incorrect study treatment at any point during Part C of the study (not the treatment to which the subject was randomized) [1].
06	Use of any prohibited medication during Parts B or C of the study [2].
07	Randomization Exclusion Criterion #6 – Current smokers at Visit C1.

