### 11.5.2. Reporting Standards

General	

 
The current GSK Integrated Data Standards Library (IDSL) will be applied for reporting, unless otherwise stated (IDSL Standards Location: https://spope.gsk.com/sites/IDSLLibrary/SitePages/Home.aspx):             
 
4.03 to 4.23: General Principles
 
5.01 to 5.08: Principles Related to Data Listings
 
6.01 to 6.11: Principles Related to Summary Tables
 
7.01 to 7.13: Principles Related to Graphics
 
 
 
All subject level listings will be located in the modular appendices as ICH listings of the GSK Clinical Study Report.
 
	
Formats	

 
Data within Part C will be reported according to the treatment each subject received for more than 50% of injections within Part C unless otherwise stated (see Section 5.1).
 
GSK IDSL Statistical Principles (5.03 & 6.06.3) for decimal places (DP's) will be adopted for reporting of data based on the raw data collected, unless otherwise stated.
 
Numeric data will be reported at the precision collected on the eCRF.
 
The reported precision (decimal places) from non eCRF sources will follow the IDSL statistical principles but may be adjusted to a clinically interpretable number of DP's.
 
	
Planned and Actual Time	

 
Reporting for tables, figures and formal statistical analyses:             
 
Nominal visits (planned time relative to dosing) will be used in figures, summaries, statistical analyses and calculation of any derived parameters, unless otherwise stated.
 
The impact of any major deviation from the planned assessment times and/or scheduled visit days on the analyses and interpretation of the results will be assessed as appropriate.
 
 
 
Reporting for Data Listings:             
 
Planned and actual time relative to study drug dosing will be shown in listings (Refer to IDSL Statistical Principle 5.05.1).
 
 
 
	

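### The primary ITT analysis assigns each subject's arm by the product received at more than half of Part C injections, and no as-randomised analysis is planned

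*SAP*

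**What the plan says.** Protocol 10.3.1 defines the ITT set by membership: "This population will consist of all randomized subjects who receive at least one dose of double-blind study medication, and will be the primary population", covering both efficacy and safety. Where randomised and received treatment differ, it asks for a profile of that subject's data. It gives no rule for grouping by treatment received.

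The SAP keeps the ITT name and membership but adds a grouping rule. Footnote 1 to SAP 4 reads: "All analyses of Part C and Part D data will be analysed according to the treatment each subject received for more than 50% of injections", counting only those given in Part C. SAP 5.1 and 11.5.2 repeat it for displays, and the SAP 7 footnote repeats it for efficacy. SAP 7.1.4 applies it to the primary endpoint: "subjects will be analysed according to the treatment each subject received for more than 50% of injections within Part C". SAP 7.2.2.1 and 7.3.2.1 carry it into the secondary and exploratory models.

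The only entry under sensitivity and supportive analyses of the primary endpoint (SAP 7.1.5.1) is: "A supportive analysis of the Per Protocol (PP) population will also be performed". Criterion 05 in SAP 11.1.1 removes from that population any subject given a product other than the randomised one at any time in Part C. In the display list, Table 2.3 is the ITT analysis, Table 2.4 the PP analysis and Tables 2.5 to 2.12 ITT subgroups; none is as randomised. SAP 2.1 declares no change from the protocol's analysis.

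**The concern.** Randomisation makes the two groups comparable; a grouping defined by later dosing need not be. The rule has three weak points:

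- A subject given the wrong product at more than half of their Part C injections moves to the other arm, taking their prognosis with them.
- A subject at exactly half meets the condition for neither arm, and no tie rule is given.
- The count covers all Part C injections. A subject who stays on double-blind treatment after a first exacerbation can have their arm decided by doses given after the event being analysed.

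The 50% threshold is fixed, but the number of wrong injections needed to cross it depends on how many were given. That in turn depends on whether the subject left Part C, and an exacerbation is one of the main reasons for leaving. The grouping variable is therefore not independent of the outcome.

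At stake is whether the superiority test of the primary endpoint rests on a randomised comparison.

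**Working it through.** **Design figure first.** Inputs from Protocol 10.2.1: 150 per arm, 40% and 60.5% with an event, 20% withdrawing before an event, true HR 0.55; two-sided 5% from Protocol 10.1.

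- Events: 0.8 × 150 × (0.40 + 0.605) = 120.6.
- HR: ln(1 - 0.40) / ln(1 - 0.605) = 0.550.
- Power (Schoenfeld): Φ(√120.6 × |ln 0.55| / 2 - 1.96) = 90.7%. Freedman's form gives 89.0%. The stated 90% is reproduced.

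**When the rule acts.** With n Part C injections, the arm changes at floor(n/2) + 1 wrong ones; for even n there is a tie at n/2.

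| Injections | Wrong to change arm | Wrong to leave no arm |
|---|---|---|
| 1 | 1 | none |
| 2 | 2 | 1 |
| 3 | 2 | none |
| 4 | 3 | 2 |
| 12 | 7 | 6 |
| 13 (C1 to C13) | 7 | none |

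Example: a subject has three correct doses, then a first exacerbation, then ten more doses of which seven are wrong. That is 7 of 13, so the arm changes, although only the randomised product had been given before the event.

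**How many subjects one wrong injection could affect.** Dosing is every 4 weeks, so a subject with at most two injections stopped before week 8. Take exponential times with yearly hazards -ln(0.395) = 0.929 (placebo), -ln(0.60) = 0.511 (mepolizumab) and dropout -ln(0.80) = 0.223. If every subject who exacerbates leaves Part C:

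- Placebo: 150 × (1 - exp(-(0.929 + 0.223) × 8/52)) ≈ 24.
- Mepolizumab: 150 × (1 - exp(-(0.511 + 0.223) × 8/52)) ≈ 16.

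If only half of those who exacerbate leave, the counts are about 15 and 11.

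**Effect on the primary result.** The documents give no error rate, so k, the number of placebo subjects mostly given mepolizumab, is assumed. Each simulated trial has 150 per arm, exponential times at the design event rates and 20% exponential dropout. The k subjects carry the mepolizumab hazard, and a Cox model is fitted by received and by randomised arm (20,000 trials per scenario).

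| k | Mean HR difference (received - randomised) | 95th percentile of absolute difference | Verdict differs |
|---|---|---|---|
| 1 | -0.002 | 0.017 | 1.6% |
| 2 | -0.004 | 0.029 | 1.7% |
| 5 | -0.010 | 0.053 | 3.2% |

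This dropout model gives about 93% power rather than 90%, so the last column is approximate.

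**Type I error under the null.** With errors unrelated to risk, one-sided rejection by received arm is 2.42% (k = 2) and 2.40% (k = 5). It rises only if errors track risk. A deliberately adverse case uses gamma frailty (mean 1, shape 2). It moves k low-risk placebo subjects to mepolizumab and k high-risk mepolizumab subjects to placebo (8,000 trials). Rejection is then 4.1% (k = 2) and 8.4% (k = 5).

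**Cost of analysing as randomised.** The sample size is unchanged. If a share e of each arm mostly received the other product, the as-randomised event proportions at e = 1% are 0.99 × 0.40 + 0.01 × 0.605 = 0.402 and 0.99 × 0.605 + 0.01 × 0.40 = 0.603. The HR becomes 0.557 and power 89.5%, against 90.7% with no errors. At e = 2% they are 0.564 and 88.3%.

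**The case against.** The strongest reply is that the condition may never arise. Allocation is by IRT (Protocol 7.2), and a designated unblinded person prepares each dose to the subject's assignment (Protocol 7.5). If nobody is mostly wrongly dosed, the two groupings are identical. Listing 9 (planned and actual treatments), Table 1.32 (PP exclusions) and the protocol's subject profile would let a reader see whether that is so.

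Subjects with one or two injections also offer few chances for error. About 21 have one and 19 have two, or 21 + 2 × 19 = 59 injections, roughly 60. At an assumed wrong-product rate of 0.1% to 1% per injection, independent between doses, that is about 0.06 to 0.6 wrong injections in the whole trial. Finally, Protocol 10.4 leaves full details of methods to the analysis plan, so the rule is arguably a permitted detail rather than a change.

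Much of this stands. The expected effect is small. The 4.1% and 8.4% figures are an upper illustration, not a forecast: nothing in the documents links preparation errors to risk. The protocol is silent on grouping, so the SAP adds to it rather than contradicting a sentence in it.

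Three things do not follow.

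- Listings and profiles reveal a discrepancy but estimate no effect. The PP analysis has correct labels for those it keeps, but it is a subset chosen after randomisation.
- The hypothetical strategy in SAP 7.1.4 is stated for discontinuation of double-blind treatment, not for wrong product.
- Errors need not be independent between doses. Syringes are filled at site and placebo is site-supplied saline (Protocol 7.1, 7.5). In Part C, Table 7 shows IRT contact only at C1, Exit and the discontinuation or withdrawal visit. A misread assignment could therefore repeat, which is how a subject would pass 50%.

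**Conclusion.** The concern holds. The primary hazard ratio is a randomised comparison only if no subject receives the wrong product at half or more of their Part C injections, and the plan contains no analysis that would restore it if one did. The size is zero without such errors. With 2 to 5 affected placebo subjects (an assumption) it is a mean shift of 0.004 to 0.010 in the hazard ratio and a changed verdict in about 2% to 3% of trials. Type I error is not inflated unless errors are related to risk.

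Open-label doses in Part D do not count towards the rule, so the planned switch does not move placebo subjects. The limits to dosed subjects and on-treatment data come from the protocol and are separate matters. The point should be fixed because the remedy is so cheap, not because a large bias is expected.

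**What to change.** Group all Part C efficacy analyses by randomised treatment. For efficacy, amend SAP 4 (footnote 1), 5.1, 7 (footnote), 7.1.4, 7.2.2.1, 7.3.2.1 and 11.5.2. Align the SAP 6.1 footnote so that baseline and disposition tables show the same groups as the efficacy tables.

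Keep the received-treatment grouping for the safety displays in SAP 8, or as a sensitivity analysis, and add a tie rule for exactly 50%, for example the randomised treatment. State which grouping the Part D columns, labelled by previous product, will use.

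If the received-treatment rule is kept for efficacy, declare it in SAP 2.1 as an addition to the protocol's ITT analysis and add an as-randomised analysis of the primary endpoint beside Table 2.3.

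The cost is SAP wording and one treatment variable in the efficacy datasets. No extra subjects, data or visits are needed.

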#### 7.1.5. Statistical Analyses / Methods

Details of the planned displays are provided in [Appendix 11](#): List of Data Displays and will be based on GSK data standards and statistical principles.

Unless otherwise specified, endpoints / variables defined in Section 7.1.1 will be summarised using descriptive statistics, graphically presented (where appropriate) and listed.

##### 7.1.5.1. Statistical Methodology Specification

Endpoint / Variables

 
Time to first clinically significant exacerbation (ADaM Dataset: ADTTE)
 

Model Specification

 
The endpoint will be compared between treatment groups using a Cox proportional hazards model. 
 
Fixed Categorical Covariates: Treatment, Region, Baseline maintenance OCS use [Visit C1]
 
Fixed Continuous Covariates: Exacerbations in the year prior to randomization [Visit C1] (as an ordinal variable)
 
 
 
See Section 5.4.1 for further details around model covariates.
 

Model Checking & Diagnostics

 
The TIES=EXACT option will be applied for the handling of ties in failure times.
 
In the event that this model fails to converge, the list of covariates may be adjusted and/or reduced.
 
Distributional assumptions underlying the model used for analysis will be examined by: 
 
assessing if a sufficient number of events occurred within covariate categories.
 
 
 
The proportional hazards assumptions will be examined by: 
 
obtaining plots of the Kaplan-Meier curves and of the log of the cumulative hazard function (log of the negative log of the estimated survivor function) against the log of the survival time
 
 
 
If there are any major important departures from the distributional or proportional hazard assumptions transformations of covariates may be considered or alternative models may be explored as supportive analysis.
 

Model Results Presentation

 
Summaries and graphs will be produced presenting the probability of an event over time by treatment group using Kaplan-Meier estimates and the corresponding 95% confidence intervals.
 

• The hazard ratio (Mepolizumab/Placebo) from the Cox proportional hazards model will be reported with the corresponding 95% CI and p-value.

Sensitivity and Supportive Analyses

• A supportive analysis of the Per Protocol (PP) population will also be performed.

Subgroup Analyses


• Subgroup analyses of the primary endpoint will be performed for the Intent-To-Treat (ITT) population and all subgroups listed within Section 5.4.2.

